3.4 Patient Identification

3.4.1 Patient Identification

The Principal Investigator or qualified designee will obtain signed, informed consent from the potential study patient before any study-specific procedures are performed.

After written informed consent has been obtained, each patient will receive a unique patient number.

PAREXEL International Statistical Analysis Plan

Medivir
Protocol: MIV-711-202

Final 1.0
16 January 2018

The patient number allocated to any patient will not be reallocated to other patients if he/she terminates the study participation for any reason, regardless of whether IMP was taken or not.

3.4.2 Allocation of Patients to Treatment

This is an open label study and all patients will receive 200 mg q.d. The first dose of IMP will be administered at Visit 2 (Enrolment) after the patient has signed the informed consent form and the Investigator has confirmed the patient's eligibility based on screening procedures performed.

3.5 Study Drug Administration

In Study MIV-711-202, all patients will receive 200 mg q.d. oral dose of MIV-711 for 26 weeks. The IMP should be taken q.d. in the morning approximately 24 hours apart. The first dose in Study MIV-711-202 is administered at the site during Visit 2 (Enrolment). All patients must stay at the site 2 hours after administration of the first dose.

IMP should be dispensed during the Visits 2 and 4 and returned by the patients for drug accountability at Visit 4 and Visit 5.

On days when the patient is visiting the site the IMP must be taken at the site under fasting conditions (and not at home) and the time of the intake must be recorded in the source documents.

3.6 Interim Analysis

No interim analysis will be conducted for any efficacy endpoint. Interim safety data will be reviewed during DMC meetings after the first 25 patients have completed Visit 4 and Visit 5. No formal statistical tests will be undertaken. Adverse events will be summarised descriptively and tabulated for all patients by treatment group. The DMC will consider the results of the AE summaries when making decisions regarding dosing of subsequent cohorts (i.e. need for dose stoppages) or the need for formal interim analysis of non-safety data.

4. Study Analysis Variables

The study variables are collected for the two studies MIV-711-201 and MIV-711-202 according to the study schedules displayed in section 4.1 and section 4.2, respectively.

PAREXEL International Statistical Analysis Plan

Medivir
Protocol: MIV-711-202

Final 1.0
16 January 2018

4.1 Study Schedule MIV-711-201

Study Visit	V1	V2	V3	V4	V5	V6	V7	V8	V9
Weeks	-4	1	2	4	8	14	20	26	30
Day	up to 30 days	Day 1	day 15 ±2 days	day 29 ±2 days	day 57 ±2 days	±7 days	±7 days	±7 days	± 7 days
Visit Description	Screening	Randomisation/ Baseline	Treatment period						Safety follow- up
Signed informed consent	X								
Randomisation		X							
Inclusion/exclusion criteria	X	X							
Target knee identification ^A	X								
Demographics	X								
Weight	X							X	
Height	X								
Medical & Surgical history	X								
Physical examination	X	X	X ^B	X ^B	X	X	X ^B	X	
Vital signs, including body temperature	X	X	X	X	X	X	X	X	X
12-Lead ECG ^C	X	X	X	X	X	X	X	X	X

PAREXEL International Statistical Analysis Plan

Medivir
Protocol: MIV-711-202

Final 1.0
16 January 2018

Study Visit	V1	V2	V3	V4	V5	V6	V7	V8	V9
Weeks	-4	1	2	4	8	14	20	26	30
Day	up to 30 days	Day 1	day 15 ±2 days	day 29 ±2 days	day 57 ±2 days	±7 days	±7 days	±7 days	± 7 days
Visit Description	Screening	Randomisation/ Baseline	Treatment period						Safety follow- up
Clinical chemistry/ Haematology	X	X	X	X	X	X	X	X	X
Urinalysis ^D	X	X	X	X	X	X	X	X	X
Urine drug screen	X				X				
Post-menopausal assessment (females only)	X								
HBsAg, anti-HBc, anti-HBs, HCV, and HIV test	X								
e-diary dispensing and training	X								
Patient Emergency Card dispense	X								
MRI of target knee ^E		X						X	
e-diary for pain and analgesic ^F		X				X		X	
Duration and onset of knee pain		X							
NRS, ICOAP, WOMAC	X ^G	X			X	X		X	X ^G

PAREXEL International Statistical Analysis Plan

Medivir
Protocol: MIV-711-202

Final 1.0
16 January 2018

Study Visit	V1	V2	V3	V4	V5	V6	V7	V8	V9
Weeks	-4	1	2	4	8	14	20	26	30
Day	up to 30 days	Day 1	day 15 ±2 days	day 29 ±2 days	day 57 ±2 days	±7 days	±7 days	±7 days	± 7 days
Visit Description	Screening	Randomisation/ Baseline	Treatment period						Safety follow- up
Global improvement (6-point Likert scale)					X	X		X	
EuroQoL EQ-5D-5L		X						X	
Brief Medication Questionnaire					X	X		X	
Dispense IMP ^J		X ^H			X	X			
Drug accountability		X			X	X		X	
PK sampling (blood)				X				X	
Biomarker samples ^J		X		X		X		X	X
AEs/SAEs monitoring	X	X	X	X	X	X	X	X	X
Concomitant Medication		X	X	X	X	X	X	X	X
Phone call to assess safety and tolerability ^K		X	X	X	X	X	X		
Blood sample for pharmacogenomics, proteomics, genomics, metabolomics and lipidomics and urine sample for proteomics and metabolomics ^L		X						X	

PAREXEL International Statistical Analysis Plan

Medivir
Protocol: MIV-711-202

Final 1.0
16 January 2018

Abbreviations: AE=Adverse event; anti-HBc=Total Hepatitis B core antibody; anti-HBs= Antibody to Hepatitis B surface antigen; ECG=Electrocardiogram; eCRF=Electronic case report form; EQ-5D-5L=EQ-5D is a standard measure of health status developed by the EuroQol Group in order to provide a simple, generic measure of health for clinical and economic appraisal; HBsAg=Hepatitis B surface antigen; HCV=Hepatitis C virus; HIV=Human immunodeficiency virus; ICOAP=Intermittent and constant osteoarthritis pain; IMP=Investigation medicinal product; K-L=Kellgren and Lawrence; MRI=Magnetic resonance imaging; NRS=Numeric rating scale; PK=pharmacokinetic(s); PRO=Patient reported outcomes; SAE=Serious adverse event; WOMAC=Western Ontario and McMaster Universities Osteoarthritis Index.

- A. Selection of target knee was to be primarily based on pain, secondarily on K-L Grade, and if both sides were equal with regard to these two criteria, the right knee was always to be prioritised.
- B. Targeted physical examination. Full physical examination at all other visits.
- C. At Visit 2 at pre-dosing, 0.5, 1 and 2 hours post-dosing (\pm 10 minutes). At all other visits 30 minutes post-dose (\pm 10 minutes).
- D. If urinalysis was positive for blood, nitrites, leukocyte esterase, and/or protein, additional microscopic analysis was to be performed.
- E. MRI was to be performed at Visit 2 (-7 days) and at Visit 8 (\pm 5 days).
- F. To be completed at home during the 2 weeks prior to the marked visit.
- G. Only NRS for average overall knee pain severity (1-week recall) for both knees.
- H. The first dose of IMP was to be dispensed to the patient at the site. Date and time was to be recorded in the eCRF. The first dose was to be given to the patient after all baseline assessments had been performed including completion of Patient Reported Outcomes (PROs). Patients were to take the IMP in the clinic in a fasting state and were required to stay at the clinic for 2 hours after intake of the IMP.
- I. Patients were to take the IMP in the clinic in a fasting state. Breakfast was to be eaten 1 hour after IMP intake. The last dose of the IMP was to be taken at the site during Visit 8.
- J. Both blood and urine samples were to be collected for biomarker. The first void of morning urine must have occurred before the urine sample was taken from a later void. The patients were to be fasting when all biomarker samples were taken.
- K. The phone call was to be made 5-9 days after all dosing visits.
- L. Blood was to be collected for pharmacogenomics, proteomics, genomics, metabolomics and lipidomics and urine was to be collected for proteomics and metabolomics pre-dose at Visit 2 (baseline) and Visit 8 from patients who provided additional written.

PAREXEL International Statistical Analysis Plan

Medivir
Protocol: MIV-711-202

Final 1.0
16 January 2018

4.2 Study Schedule MIV-711-202

Study Visit	V1	V2	V3	V4	V5	V6
Weeks	-2	1	4 ±2 days	14 ±7 days	26 ± 7 days	30 ± 7 days
Day	-10 ± 5 days	Day 1	28 ±2 days	98 ±7 days	182 ± 7 days	210 ± 7 days
Visit Description	Screening^A	Enrolment	Safety	Safety and Treatment		Safety follow-up
Signed informed consent	X	X ^B				
Inclusion/exclusion criteria	X	X				
Demographics	X					
Weight	X					
Medical & Surgical history	X					
Physical examination	X ^C	X	X	X	X	
Vital signs, including body temperature	X ^C	X	X	X	X	X
12-Lead ECG ^D	X ^C	X ^E	X	X	X	X
Clinical chemistry/Haematology	X ^C	X	X	X	X	X
Urinalysis ^F	X ^C	X	X	X	X	X
Urine drug screen	X					
Post-menopausal assessment (females only)	X					
e-diary dispensing and training		X				

PAREXEL International Statistical Analysis Plan

Medivir
Protocol: MIV-711-202

Final 1.0
16 January 2018

Study Visit	V1	V2	V3	V4	V5	V6
Weeks	-2	1	4 ±2 days	14 ±7 days	26 ± 7 days	30 ± 7 days
Day	-10 ± 5 days	Day 1	28 ±2 days	98 ±7 days	182 ± 7 days	210 ± 7 days
Visit Description	Screening ^A	Enrolment	Safety	Safety and Treatment		Safety follow-up
e-diary for pain and analgesic ^G				X	X	
Patient Emergency Card Dispensing	X					
MRI of the bone area					X ^H	
Registration in the IWRS	X					
NRS, ICOAP, WOMAC				X	X	
Global improvement (6-point Likert scale)				X	X	
EuroQoL EQ-5D-5L					X	
Brief Medication Questionnaire				X	X	
Dispense IMP ^I		X ^J		X		
Drug accountability				X	X	
e-diary return					X	
PK sampling (blood)					X	
Biomarker samples ^K		X		X	X	X
AEs/SAEs monitoring	X	X	X	X	X	X

PAREXEL International Statistical Analysis Plan

Medivir
Protocol: MIV-711-202

Final 1.0
16 January 2018

Study Visit	V1	V2	V3	V4	V5	V6
Weeks	-2	1	4 ±2 days	14 ±7 days	26 ± 7 days	30 ± 7 days
Day	-10 ± 5 days	Day 1	28 ±2 days	98 ±7 days	182 ± 7 days	210 ± 7 days
Visit Description	Screening ^A	Enrolment	Safety	Safety and Treatment		Safety follow-up
Concomitant Medication		X	X	X	X	X
Phone call to assess safety and tolerability ^L		X	X	X	X	
Blood sample for pharmacogenomics, proteomics, genomics, metabolomics and lipidomics and urine sample for proteomics and metabolomics					X ^M	

Abbreviations: AE=adverse event; ECG=electrocardiogram; eCRF=electronic case report form; DNA=deoxyribose nucleic acid; EuroQoL EQ-5D-5L= a standard measure of health status developed by the EuroQoL Group in order to provide a simple, generic measure of health for clinical and economic appraisal; FSH=follicle stimulating hormone; ICF=informed consent form; ICOAP=intermittent and constant osteoarthritis pain; IMP=investigational medicinal product; IWRS= Interactive Web Response System; MRI=magnetic resonance imaging; NRS=numeric rating scale; PK=pharmacokinetic; PRO=patient-reported outcomes; RNA=ribonucleic acid; SAE=serious adverse event; WOMAC= Western Ontario and McMaster Universities Osteoarthritis Index

- A) The Screening visit (Visit 1) will coincide with 26-week End of Treatment visit of Study MIV-711-201 (Visit 8).
- B) Optional ICF to be provided and signed at Visit 2.
- C) Assessed at Visit 8 in Study MIV-711-201. Only need to be re-assessed if Visit 8 does not occur on the same day as Visit 1 in Study MIV-711-202
- D) 30 minutes post-dose (± 10 minutes).
- E) 12-lead serial ECGs will be recorded at Visit 2 (Enrolment) pre-dosing and after 30 minutes, 1 hour and 2 hours post-dosing (± 10 minutes).
- F) If urinalysis is positive for blood, nitrites, leukocyte esterase, and/or protein, additional microscopic analysis may be performed.
- G) To be completed at home during the 2 weeks leading up to the marked visit with final recording the day before.
- H) ± 5 days
- I) Patients take IMP in the clinic in a fasting state. Breakfast can be eaten 1 hour after IMP intake. The last dose of the IMP will be taken at the site during Visit 5.
- J) The first dose of IMP will be dispensed to the patient at the site and the patient must stay at the clinic for 2 hours after intake of IMP. Date and time should be recorded in the

PAREXEL International Statistical Analysis Plan

Medivir
Protocol: MIV-711-202

Final 1.0
16 January 2018

Study Visit	V1	V2	V3	V4	V5	V6
Weeks	-2	1	4 ±2 days	14 ±7 days	26 ± 7 days	30 ± 7 days
Day	-10 ± 5 days	Day 1	28 ±2 days	98 ±7 days	182 ± 7 days	210 ± 7 days
Visit Description	Screening^A	Enrolment	Safety	Safety and Treatment		Safety follow-up

eCRF. The first dose should be given to the patient after all assessments at Enrolment have been performed.

- K) Both blood and urine sample will be collected for biomarkers. The first void of morning urine should have occurred before the urine sample is taken from a later void. The patients must be fasting when all biomarker samples are taken.
- L) The phone call should be made 5-9 days after all dosing visits. There will be additional phone calls at Week 10 and Week 20.
- M) Blood will be collected for pharmacogenomics, proteomics, genomics, metabolomics and lipidomics and urine will be collected for proteomics and metabolomics pre-dose at Visit 5 from patients who provide additional written consent.

PAREXEL International Statistical Analysis Plan

Medivir
Protocol: MIV-711-202

Final 1.0
16 January 2018

4.3 Demographic and Background Variables

The following demographic and anthropometric information will be recorded at screening:

- Date of informed consent
- Medical and surgical history (including previous and current medical conditions and medications)
- Age calculated as (date of informed consent – date of birth)/365.25
- Gender
- Ethnic origin
- Race
- Height (cm)
- Body weight (kg)
- Body mass index (BMI) (kg/m^2)

Adverse Events from MIV-711-201 will be recorded as Medical history in MIV-711-202.

Concomitant medication in MIV-711-201 will be recorded as prior medication in MIV-711-202.

4.4 Safety Variables

4.4.1 Adverse Events

All AEs and SAEs will be recorded in the eCRF system from the date the informed consent form is signed (visit 1) until the safety follow up visit (visit 6) is completed.

4.4.2 Clinical Laboratory Tests

Blood samples for hematology and clinical chemistry, and urinalysis assessments will be collected during all study visits: Visit 1 (screening), Visit 2 (Week 1), Visit 3 (Week 4), Visit 4 (Week 14), Visit 5 (Week 26), Visit 6 (Week 30, follow-up).

The following safety laboratory parameters will be measured:

Hematology: WBC and differential, % and absolute for: neutrophils, lymphocytes, monocytes, eosinophils, basophils; hemoglobin, hematocrit, RBC, RBC indices (MCV, MCH and MCHC) and morphology, platelet count

PAREXEL International Statistical Analysis Plan

Medivir
Protocol: MIV-711-202

Final 1.0
16 January 2018

Chemistry: urea nitrogen, creatinine, calcium, sodium, potassium, bicarbonate, chloride, total protein, fasting glucose, total bilirubin, direct bilirubin and indirect bilirubin, ALT, AST, alkaline phosphatase, GGT, CPK, CRP.

Urinalysis: with microscopic: specific gravity, pH, protein, glucose, ketones, nitrites, blood and leukocyte esterase

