## 7 ENDPOINT AND METHODS OF ASSESSMENT

### 7.1 Primary Endpoint (Study Population A)

The primary objective is to study the safety and tolerability of MIV-711 in OA patients who have received treatment for up to 52 (26+26) weeks.

Safety endpoints:

- Incidence and severity of AEs
- Incidence and severity of clinical laboratory abnormalities
- Physical examination findings by patient
- Incidence and severity of ECG abnormalities
- Mean change from Baseline (Visit 2 of Study MIV-711-201) in vital signs (blood pressure, heart rate, temperature) and oxygen saturation
- Categorical summary of observed vital signs and vital sign changes compared to Baseline (Visit 2 of Study MIV-711-201), by patient

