**Table 1: Clinical Laboratory Testing**

Post-menopausal determination: Follicle stimulation hormone (FSH) Female patients must be of non-childbearing potential either as naturally (spontaneously) post-menopausal or due to hysterectomy and/or bilateral oophorectomy/salpingo-oophorectomy (as determined by patient medical history). Naturally (spontaneously) post-menopausal is defined as being amenorrheic for 12 months without an alternative medical cause and with a Screening FSH indicating post-menopausal state.

Fasting samples are required at all study visits as fasting glucose is required as part of the chemistry samples.

Haematology: WBC and differential, % and absolute for: neutrophils, lymphocytes, monocytes, eosinophils, basophils; haemoglobin, haematocrit, RBC, RBC indices (MCV, MCH and MCHC) and morphology, platelet count

Chemistry: urea nitrogen, creatinine, calcium, sodium, potassium, bicarbonate, chloride, total protein, fasting glucose, total bilirubin, direct bilirubin and indirect bilirubin, ALT, AST, alkaline phosphatase, GGT, CPK, CRP

Urinalysis: with microscopic: specific gravity, pH, protein, glucose, ketones, nitrites, blood and leukocyte esterase

Urine Drug Screen: Amphetamine, Benzodiazepines, THC, Cocaine, Oxycodone and Opiate

PTH (parathyroid hormone)

The above parameters will be analysed by a Central Laboratory. Total blood volumes to be collected are detailed in Appendix 1. Further details on the provider and handling of laboratory samples will be provided in the Laboratory Manual.

The study schedule is summarised in Table 2.

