9.2 Clinical Safety Laboratory Tests (Hematology, Chemistry, Urinalysis)

9.2.1 Hematology and Chemistry

A by-patient listing of all observed chemistry and hematology laboratory data will be provided. Laboratory results outside the normal range will be flagged. The abnormal values will be flagged with ‘L’ (low) for values below the lower limit of the laboratory’s normal range or ‘H’ (high) for values above the upper limit of the laboratory’s normal range. Abnormal values will be graded as not clinically significant (NCS) or clinically significant (CS). Clinically significant laboratory results will be included in the AE listings.

The observed values of all safety laboratory assessments for clinical chemistry and hematology will be summarized using descriptive statistics showing the number of

PAREXEL International Statistical Analysis Plan

Medivir
Protocol: MIV-711-202

Final 1.0
16 January 2018

observations (n), mean, median, SD, minimum, and maximum value. Table summaries will be presented by time point.

Baseline values for all clinical chemistry and hematology parameters will be categorized as being below the normal range (Low), within the normal range (Normal), and above the normal range (High). In addition, the minimum and maximum score over visits post baseline will be calculated and categorized into Low, Normal and High. Note that the minimum/maximum are taken over visits post the baseline visit, i.e. visits when the patients are on 200 mg MIV-711. Shift from baseline tables of the minimum category score and the maximum category score will be tabulated displaying frequency counts and percentage of patients in each (low, normal, high)-matrix by study group.

All hematology, chemistry, and coagulation, laboratory parameters noted in Section 4.4.2 of this SAP will be tabulated.

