9.2.2 Urinalysis

Urinalysis test results will be listed. All positive findings in the microscopic examination will be listed.

Observations outside the normal range will be flagged. The abnormal quantitative values will be flagged with 'L' for values below the lower limit of the laboratory's normal range, 'H' for values above the upper limit of the laboratory's normal range, or 'Ab' for abnormal qualitative test results. All original and unscheduled assessments will be listed.

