Table 14.3.1.6	Number and Percentage of Patients with Treatment Emergent Adverse Events by Frequency, Preferred Term, and Group
Table 14.3.2.1	Clinical Laboratory Chemistry Summary of Observed Values, SAF Population
Table 14.3.2.2	Clinical Laboratory Hematology Summary of Observed Values, SAF Population
Table 14.3.2.3	Clinical Laboratory Chemistry – Shift From Baseline to Maximum Value, SAF Population
Table 14.3.2.4	Clinical Laboratory Chemistry – Shift From Baseline to Minimum Value, SAF Population
Table 14.3.2.5	Clinical Laboratory Hematology – Shift From Baseline to Maximum Value, SAF Population
Table 14.3.2.6	Clinical Laboratory Hematology – Shift From Baseline to Minimum Value, SAF Population
Table 14.3.3	Vital Signs Blood Pressure and Heart Rate Summary of Observed and Change from Baseline Values, SAF Population
Table 14.3.4.1	12 Lead ECG – Summary of Observed and Change from Baseline Values SAF Population
Table 14.3.4.2	12-Lead ECG – Categorical Summary of Observed Values, SAF Population
Table 14.3.4.3	12-Lead ECG – Categorical Summary of Change From Baseline, SAF Population

PAREXEL International Statistical Analysis Plan

Medivir
Protocol: MIV-711-202

Final 1.0
16 January 2018

12. Figures

TLF Number	Title
Figure 14.2.1.1	Estimated Mean \pm 95% CI for MRI of Bone Area by Week and Group, ITT Population
Figure 14.2.1.2	Estimated Mean \pm 95% CI for MRI of Cartilage Thickness by Week and Group, ITT Population
Figure 14.2.1.3	Estimated Mean \pm 95% CI for MRI of Total BML Volume by Week and Group, ITT Population
Figure 14.2.1.4	Estimated change from Visit 2 MIV-711-201 \pm 95% for MRI of Bone Area by Week and Group, ITT Population
Figure 14.2.1.5	Estimated change from Visit 2 MIV-711-201 \pm 95% for Cartilage Thickness by by Week and Group, ITT Population
Figure 14.2.1.6	Estimated change from Visit 2 MIV-711-201 \pm 95% for MRI of Total BML Volume by Week and Group, ITT Population
Figure 14.2.1.7	Estimated change from Visit 2 MIV-711-201 \pm 95% for MRI of Bone Area by Week and Group, PPS Population
Figure 14.2.1.8	Estimated change from Visit 2 MIV-711-201 \pm 95% for Cartilage Thickness by Week and Group, PPS Population
Figure 14.2.1.9	Estimated change from Visit 2 MIV-711-201 \pm 95% for MRI of Total BML Volume by Week and Group, PPS Population
Figure 14.2.3.1	Estimated Mean \pm 95% CI for NRS Items by Week and Group, ITT Population

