Listing 16.2.6.20	Brief Medication Questionnaire
Listing 16.2.6.21	E-Diary Assessments over the Last 12 Hours
Listing 16.2.6.22	E-Diary Assessments – Derived Results for each Study Visit
Listing 16.2.6.23	Efficacy Biomarkers from Serum and Urine Samples
Listing 16.2.6.24	Time-Integrated Concentrations (TIC) and Their Z-scores for Efficacy Biomarkers from Serum and Urine Samples
Listing 16.2.7.1	Adverse Events
Listing 16.2.7.2	Serious Adverse Events
Listing 16.2.7.3	Adverse Events Leading to Discontinuation
Listing 16.2.8.1	Clinical Laboratory Chemistry – Observed Values
Listing 16.2.8.2	Clinical Laboratory Hematology – Observed Values
Listing 16.2.8.3	Clinical Laboratory Urinalysis – Observed Values
Listing 16.2.8.4	Clinical Laboratory Urinalysis – Positive Microscopic Findings
Listing 16.2.8.5	Vital Signs Observed Values
Listing 16.2.8.6	Vital Signs Change from Baseline
Listing 16.2.8.7	Vital Signs Overall Qualitative Results Abnormal Assessments
Listing 16.2.8.8	12 Lead ECG Quantitative Findings
Listing 16.2.8.9	12 Lead ECG Change From Baseline
Listing 16.2.8.10	12 Lead ECG Overall Qualitative Assessment
Listing 16.2.8.11	Physical Examination Abnormal Findings
Listing 16.2.8.12	Phone Call to Assess Safety

PAREXEL International Shells

Medivir
Protocol: MIV-711-202

Final 1.0
16 January 2018

14. Table Shells

PAREXEL International SAP Amendment Shells

Medivir
Protocol: MIV-711-202

Final 1.0
16 January 2018

Medivir
Protocol Number: MIV-711-202

Page X of Y

Table 14.1.1
Patient Disposition
All Enrolled Patients

	Group A N = x	Group B N = x
Number Patients Enrolled	nn (nn.n%)	nn (nn.n%)
Completed Study	nn (nn.n%)	nn (nn.n%)
Discontinued from Study	nn (nn.n%)	nn (nn.n%)
Number Patients in ITT	nn (nn.n%)	nn (nn.n%)
Number Patients in PPS	nn (nn.n%)	nn (nn.n%)
Number Patients in SAF	nn (nn.n%)	nn (nn.n%)
Reason for Discontinuation		
Adverse Event	nn (nn.n%)	nn (nn.n%)
Protocol Deviation	nn (nn.n%)	nn (nn.n%)
Consent Withdrawn	nn (nn.n%)	nn (nn.n%)
Lost to Follow-Up	nn (nn.n%)	nn (nn.n%)
Death	nn (nn.n%)	nn (nn.n%)
Other	nn (nn.n%)	nn (nn.n%)

PAREXEL International SAP Amendment Shells

Medivir
Protocol: MIV-711-202

Final 1.0
16 January 2018

Medivir
Protocol Number: MIV-711-202

Page X of Y

Table 14.1.2
Demographics - Continuous Variables
ITT Population

	Statistic	Group A N = x	Group B N = x
	n	nn	nn
Age (years)	Mean	xx.x	xx.x
	SD	xx.xx	xx.xx
	Median	xx.x	xx.x
	Min	xx	xx
	Max	xx	xx
	n	nn	nn
Height (cm)	Mean	xx.x	xx.x
	SD	xx.xx	xx.xx
	Median	xx.x	xx.x

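### Urinalysis is a safety laboratory panel under a primary endpoint, yet the SAP lists it and never tabulates it

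*SAP*

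**What the plan says.** **Endpoint.** Protocol 7.1 lists, among the primary safety endpoints for Study Population A, "Incidence and severity of clinical laboratory abnormalities". Protocol 9.5.1 repeats the item and says that safety will be assessed descriptively in summary tables over time. Protocol 7.3 makes the same endpoints secondary for Study Population B. None of these sections names or excludes a laboratory panel.

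**Collection.** Protocol Table 1 (Clinical Laboratory Testing) includes urinalysis: "with microscopic: specific gravity, pH, protein, glucose, ketones, nitrites, blood and leukocyte esterase". SAP 4.4.2 carries the panel over ("Urinalysis: with microscopic: specific gravity, pH, protein, glucose, ketones, nitrites, blood and leukocyte esterase") and states that "Blood samples for hematology and clinical chemistry, and urinalysis assessments will be collected during all study visits".

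**Analysis.** SAP 9.2.1 gives hematology and chemistry descriptive summaries by time point and shift tables by group. SAP 9.2.2 says of the third panel: "Urinalysis test results will be listed. All positive findings in the microscopic examination will be listed". It adds flags for low, high or qualitatively abnormal values, but no summary.

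**Protocol summary plan.** Protocol 9.5.4 names haematology and serum chemistry as the laboratory tests to be summarised at each scheduled assessment. It then says that potentially clinically important findings will be both summarised and listed.

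**A stray word.** SAP 9.2.1 closes with: "All hematology, chemistry, and coagulation, laboratory parameters noted in Section 4.4.2 of this SAP will be tabulated". Section 4.4.2 contains no coagulation test.

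**The concern.** The study has no concurrent control and no hypothesis test (protocol 9.2.1 and 9.5.4), so its answer on safety is a set of descriptive counts. For two laboratory panels those counts are planned. For the third they are not, although the endpoint wording covers laboratory abnormalities without restriction and protocol Table 1 places urinalysis among the clinical laboratory tests.

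At stake is how often a patient with a normal baseline develops an abnormal result, such as protein, blood or glucose in the urine, while taking MIV-711. If the investigator judges the change not clinically significant, it appears only in a patient listing. Anyone who wants the incidence by group would have to count it by hand.

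**Working it through.** There is no sample-size or error-rate figure to reproduce. The check follows each panel from collection to planned output, then sizes what goes untabulated.

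**Step 1: outputs by panel.** Tables are from the SAP section 11 index and the section 14 shells; listings are from section 13 and the section 15 shells.

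| Panel | Collected (protocol Table 1, SAP 4.4.2) | Summary tables | Listings |
|---|---|---|---|
| Chemistry | yes | 3 (14.3.2.1, 14.3.2.3, 14.3.2.4) | 1 (16.2.8.1) |
| Hematology | yes | 3 (14.3.2.2, 14.3.2.5, 14.3.2.6) | 1 (16.2.8.2) |
| Urinalysis | yes | 0 | 2 (16.2.8.3, 16.2.8.4) |
| Coagulation | no | 0 | 0 |

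The last laboratory table in the index is "Clinical Laboratory Hematology – Shift From Baseline to Minimum Value, SAF Population". The last urinalysis output is the listing "Clinical Laboratory Urinalysis – Positive Microscopic Findings".

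**Step 2: other routes to a count.** Protocol 7.13.1 includes abnormal laboratory findings among adverse events. Protocol 10.6 makes a laboratory change judged clinically significant an adverse event. Such a urinalysis change would reach the treatment-emergent adverse event tables by group (SAP 9.1). A change judged not clinically significant has no such route. SAP 9.2.1 says that clinically significant results enter the adverse event listings; SAP 9.2.2 does not repeat this for urinalysis.

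**Step 3: scale.** Inputs:
- 8 parameters: specific gravity, pH, protein, glucose, ketones, nitrites, blood, leukocyte esterase (SAP 4.4.2).
- 3 on-drug visits after the first dose in MIV-711-202: Visits 3, 4 and 5 (SAP 4.2). The last dose is taken at Visit 5, so Visit 6 is off drug.
- 50 to 80 patients anticipated, Groups A and B together (protocol 5.4).

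Results = parameters x visits x patients:
- 8 x 3 x 50 = 1,200
- 8 x 3 x 80 = 1,920

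These assume no dropout. Group A adds the on-drug visits of Study MIV-711-201. SAP 4.1 schedules urinalysis there at Visits 3 to 8, which is 6 visits, so 8 x 6 = 48 further results per Group A patient. The documents do not split the expected 50 to 80 by group, so no Group A total is given.

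**Step 4: what a table would need.** SAP 9.2.2 already specifies the H, L and Ab flags. The shell for Listing 16.2.8.3 already carries the NCS/CS classification. SAP section 9 already sets the safety baselines, and both schedules show urinalysis at those visits (MIV-711-201 Visit 2 for Group A, MIV-711-202 Visit 2 for Group B).

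**The case against.** The strongest reply is that the SAP does what the protocol asks. Protocol 9.5.4 is the only protocol text that names the laboratory tests to be summarised, and it names the two panels that the SAP tabulates. This stands in part. A reader might infer that the SAP departed from the protocol; the documents do not support that, because both summary plans omit urinalysis. What remains is that the endpoint in protocol 7.1 and 9.5.1, read with Table 1, is wider than either plan, and neither document says that urinalysis is excluded.

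The second reply is that important findings are counted anyway. A reader might infer that new proteinuria, haematuria or glucosuria could be found only by reading listings. That goes too far: protocol 7.13.1 and 10.6 carry clinically significant changes into the adverse event tables. The gap is limited to abnormalities judged not clinically significant. Those are still part of an endpoint about abnormalities, and the judgement is made by the investigator in an open-label study.

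The third reply concerns coagulation. A reader might infer that the SAP tabulates a coagulation panel in place of urinalysis. It does not. The sentence in 9.2.1 covers only parameters noted in 4.4.2, where there are none, and no coagulation table or listing exists. The word is an editorial slip and does not cause the urinalysis gap.

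Lastly, a count that includes Visit 6 would give 8 x 4 x 50 = 1,600 to 8 x 4 x 80 = 2,560. That is not a count of on-drug results. Either range counts raw results, not abnormalities, and none of those results is lost, since all are listed.

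**Conclusion.** The point holds in a limited form. If the plan is followed as written, no output gives the number or percentage of patients with an abnormal urinalysis result. For abnormalities not judged clinically significant, no incidence is reported for Group A, where the endpoint is primary, or for Group B, where it is secondary. About 1,200 to 1,920 on-drug results in MIV-711-202, plus 48 per Group A patient from MIV-711-201, are listed and not tabulated.

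This rests on reading the endpoint as covering every panel in protocol Table 1. If the sponsor meant hematology and chemistry only, the documents should say so. The figures assume the anticipated enrolment and full attendance. Severity is minor: no estimate or error rate changes, and the raw data remain available.

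**What to change.** In SAP 9.2.2 and section 11, add one table on the SAF population, by group. For each urinalysis parameter it should give n (%) of patients with a normal baseline and any on-treatment abnormal result, using the existing H, L and Ab flags and split by NCS/CS. The split is the nearest thing to severity that the listing shell already carries. Use the SAP section 9 safety baselines: MIV-711-201 Visit 2 for Group A and MIV-711-202 Visit 2 for Group B.

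State which visits count as on treatment. For Group A, the MIV-711-202 Visit 2 sample follows a dosing gap of 10 ± 5 days, and Visit 6 is off drug for both groups.

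Separately, delete the word coagulation from SAP 9.2.1. Do not replace it with urinalysis: that section prescribes means, SDs and low/normal/high shifts, which do not suit qualitative dipstick results.

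If the sponsor prefers no table, state in the SAP that the laboratory endpoint covers hematology and chemistry only, and declare this in the study report. The cost of the main fix is one extra table.
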